The mortality status of the exposed cohort and the randomly selected controls will be ascertained using multiple techniques including; telephone interviews with subjects or their families, a review of Death Benefits claims filed with the VA, acquisition of death certificates on all known deceased individuals and reviews of autopsy reports and medical records whenever possible.

D. Morbidity Study

(1) General Considerations

A vigorous attempt to determine the morbidity experience of all exposed subjects and their primary controls will be undertaken using questionnaires, indepth personal interviews, and physical examinations. The schedule and method of contact with the study subjects is depicted in the Appendix, Table A-5.

(2) Questionnaire Methods

All exposed members and their matched primary controls will be offered a comprehensive personal and family health questionnaire via telephone. The telephone questionnaire is an important part of this study because non-compliance rates for the physical examination and its face-to-face interview are expected to be substantially greater than non-compliance with the telephone questionnaire. As depicted in the Appendix, Figure A-2, only an estimated 40% of the RANCH HAND population will participate in the examination, while 65% will respond to the telephone questionnaire. The information collected by questionnaire from these additional 309 individuals and their controls will provide valuable morbidity data which would otherwise be lost. The questionnaire (see Section XIII) will emphasize identification data, RVN tour history, dermatologic conditions, neuropsychiatric conditions, fertility aberrations, genetic defects in offspring, sensory defects, and personality factors, including assessments of risk-taking behavior. A review of medical systems will be included in the questionnaire, and will inventory symptoms prior to, during, and after duty in RVN as well as those currently manifested. The questionnaire will be limited to a 30-45 minute telephonic interaction with participants, and it will take 10 to 12 months to complete all initial questionnaires on both groups. It may be necessary to conduct the questionnaire in two telephone sessions to minimize fatigue and maximize response. The

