questionnaire will be "field-tested" on a group of 25 to 30 former Air Force pilots with RVN combat experience. Specific questions on the questionnaire will be directed to verifiable information, wherever possible. Specific response verification and bias indicator questions (nonsense symptoms), and indicators of risk-taking behavior are being developed. They will be added and appropriately sequenced immediately prior to the start of the study. Questionnaire data will be cross-linked and integrated with medical record information and physical examination findings. Questionnaire data from individuals not completing all phases of the study will not be discarded, but will be incorporated within the entire data base where statistically appropriate. Each participant will be asked to sign release forms so that all civilian health records, including those of dependents, can be obtained and reviewed as necessary. Federal health records on all family members on file in the NPRC will be retrieved. For retired members, and separated members with VA privileges, all available VA medical records will be obtained. All retrieved medical records will be reviewed, scored, compared to questionnaire data for reliability, and then be entered into a repository system. Identified participants who are non-responsive to questionnaire will be pursued to determine status, disinterest, moribund state or death, etc. These individuals will be cross-referenced in other federal record systems in an attempt to achieve total ascertainment. Death certificates and autopsy reports will be retrieved on all dead exposed and matched control subjects for the mortality analysis. Birth/death certificates will be sought for all offspring, born subsequent to the study subject's RVN duty.

(3) Physical Examination

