1	N ₁₁	N ₁₂	N ₁₃	N ₁₄
2	N ₂₁	N ₂₂	N ₂₃	N ₂₄
3	N ₃₁	N ₃₂	N ₃₃	N ₃₄
4	N ₄₁	N ₄₂	N ₄₃	N ₄₄

Analysis of Fertility/Reproduction Data. The herbicides under consideration in this study have been alleged to effect fertility and/or reproductive functioning. An attempt will be made to address these allegations by analyzing at least three primary variables: the total number of conceptions since exposure in RVN, the number of miscarriages in spouses since exposure in RVN and, the number of abnormal offspring since exposure in RVN. The study questionnaire will provide the number of miscarriages, abnormal offspring and of live births. The sum of the number of miscarriages,

still births, and live births will provide an estimate of the total number of conceptions. If differing divorce rates are found in the RANCH HAND and control groups, this may render the average number of years of marriage and the distribution of the years of marriage different in the two groups. This will be investigated and adjusted for if need be, either by analyzing total number of conceptions divided by (or normalized by) the number of years of marriage, or by using a more detailed covariance analysis. Further, the ratio of the number of miscarriages to adjusted total conceptions will be calculated and compared as will be the ratio of the number of abnormal births and adjusted total conceptions.

In summary, the following statistics relating to fertility will be calculated and analyzed at the very least:

$$\text{TOTAL CONCEPTIONS} = \# \text{Live Births} + \# \text{Still Births} + \# \text{Miscarriages}$$

$$\text{NORMALIZED FERTILITY INDEX} = \frac{\text{TOTAL CONCEPTIONS}}{\text{YEARS OF MARRIAGE}}$$

$$\text{MISCARRIAGE FRACTION} = \frac{\# \text{ MISCARRIAGES}}{\text{TOTAL CONCEPTIONS}}$$

$$\text{ABNORMALITY FRACTION} = \frac{\# \text{ ABNORMAL OFFSPRING}}{\text{TOTAL CONCEPTIONS}}$$

E. Survival Analysis

This section extends and complements sections C and D. The defining common attribute of the techniques discussed in this section is that they deal with events which (a) correspond to categorical changes in health status, and (b) occur at definite and observable times. These methods may, therefore, be applied to studies of mortality (as the name "survival analysis" implies) as well as to studies in morbidity.

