Preliminary information will be obtained from a short mail-back questionnaire during the first contact with the study subjects. Personal identification data, RVN tour information, willingness to participate, acknowledgement of the Privacy Act Statement and an Informed Consent for release of records and medical evaluation/emergency treatment will be obtained at that time. This information will be verified by review of the individual's military personnel records. Addresses and telephone numbers will be verified and updated by use of several sources (i.e., Worldwide Locator Service, Social Security Service, Credit Bureaus, Rosters of RANCH HAND Association, Veterans Administration Benefits Records, the Internal Revenue Service, and other available sources). In addition, at this time a request will be made to have the wife present for the telephone interview in order to obtain an accurate obstetrical history.

The telephone questionnaire will, of necessity, be lengthy, but it will be convenient to the subject, and given in two interviews if necessary. It will verify personal identification data such as name, SSAN/AFSN, date of birth, address, telephone numbers, race, military status, effective date of status, location of military medical records and marital history information. RVN tour information will be rechecked and expanded to include data such as date of tour, tour end date, AFSC, organization of assignment, PCS and TDY status, combat missions, medal(s) awarded (i.e., Air Medal, Distinguished Flying Cross, Purple Heart), and whether or not the tour was a RANCH HAND affiliated tour.

Pre and Post-RVN exposure information, both occupational and avocational, to asbestos, radiation, herbicides, pesticides, will be elicited, including the frequency and time of the exposure. RVN exposure to these chemical and physical agents will also be collected.

Medical information obtained during this telephone interview will include of a statement of general health, smoking history, alcohol consumption history and long-term medication/drug use. In addition, questions dealing with infertility, birth defects of offspring, as well as the wife's obstetrical history (i.e., total conceptions, live births, miscarriages, stillbirths and premature pregnancies) will be asked. A family history specifying cancer, heart disease, liver disease and inherited disorders in both the subject's and wife's families will be collected.

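### The primary reproductive variables count only post-RVN events; the pre-RVN pregnancies that the undated obstetrical history should also hold are not used as a baseline or as a check on over-reporting

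*Protocol*

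**What the plan says.** Protocol VI.D, in the paragraph on fertility and reproduction data, sets at least three primary variables. Two are "the total number of conceptions since exposure in RVN, the number of miscarriages in spouses since exposure in RVN"; the third is "the number of abnormal offspring since exposure in RVN". On the source it says: "The study questionnaire will provide the number of miscarriages, abnormal offspring and of live births".

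The one adjustment named concerns differing divorce rates and hence differing years of marriage: "This will be investigated and adjusted for if need be", either by dividing conceptions by years of marriage or by a covariance analysis. The summary formulas that follow (total conceptions, normalized fertility index, miscarriage fraction, abnormality fraction) carry no time limit.

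Section XIII says that "the wife's obstetrical history (i.e., total conceptions, live births, miscarriages, stillbirths and premature pregnancies) will be asked", with no restriction to the time after RVN. For symptoms, V.D(2) is explicit that the questionnaire "will inventory symptoms prior to, during, and after duty in RVN as well as those currently manifested". On verification, V.D(2) says: "Birth/death certificates will be sought for all offspring, born subsequent to the study subject's RVN duty".

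Matching (V.B(4)) is on age, AFSC, length of time in Vietnam and race. VIII.D names false positive response as the expected primary bias.

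**The concern.** The outcomes are largely self-reported, the exposed group knows its status, and over-reporting is the bias the protocol fears most. In that setting the couples' reproductive history before RVN has two uses. As a baseline, it shows family size already reached and any tendency to miscarry, neither of which is matched. As a negative control, it covers a period before the RVN exposure under study, so a RANCH HAND excess there would point to differential reporting, selection, other exposures or chance.

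The protocol itself shows why a baseline matters. In IV.G it reports that surveillance of spontaneous abortions at Seveso was hampered by the lack of valid pre-accident baselines, and it criticises the Oregon study for uneven ascertainment of abortions. Here a baseline appears to be within reach, but VI.D gives it no role.

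Miscarriage is the most exposed outcome. The primary correction for response bias in VIII.D is the physical examination, which cannot confirm a wife's past miscarriage. Birth and death certificates will generally not document one either.

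**Working it through.** The protocol gives no event rate, effect size or power for any reproductive variable, so there is no stated figure to reproduce. The point rests on the text; the arithmetic below only shows size, on assumed inputs.

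**1. The text side by side.** VI.D: post-RVN counts, questionnaire source, adjustment for years of marriage. XIII: obstetrical history with no date limit. V.B(4): no matching on parity or reproductive history. VIII.D: corrections by examination, verification and bias-indicator questions, and record cross-checks. No section uses pre-RVN pregnancies as covariate, contrast or negative control.

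**2. What over-reporting alone can produce.** Let p be the true event rate in both groups and f the false positive rate among exposed men only. The apparent relative risk is (p + f(1 − p))/p. For example, p = .10 and f = .02 give (.10 + .018)/.10 = 1.18.

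| p | f = .01 | f = .02 | f = .05 |
|---|---|---|---|
| .05 | 1.19 | 1.38 | 1.95 |
| .10 | 1.09 | 1.18 | 1.45 |
| .15 | 1.06 | 1.11 | 1.28 |

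If p and f are the same for pre-RVN pregnancies, the pre-RVN ratio shows the same excess and the ratio of the two ratios is 1.00. If the false reports concern post-RVN pregnancies only, the pre-RVN ratio is 1.00 and the check shows nothing.

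**3. How precise the negative control would be.** Couples per group: 780 = .65 × 1200 (questionnaire response in V.D(2), population in V.B(1)), or 450 (the number of pairs discussed in VI.F). Assumed: 1.5 pre-RVN conceptions per couple and a 15% miscarriage fraction. Control events are c = n × 1.5 × .15; with a true reported ratio of 1.20, SE(log ratio) = √(1/c + 1/(1.2c)). Two-sided 5% power is Φ(ln 1.20/SE − 1.96), with ln 1.20 = .182.

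- n = 780: c = 175.5, SE = .102, z = 1.78, power about 43%.
- n = 450: c = 101.25, SE = .135, z = 1.35, power about 27%.

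The two assumed rates matter only through their product, .225 events per couple. At .10 (1.0 × 10%), power is about 22% (n = 780) or 15% (n = 450). At .40 (2.0 × 20%), it is about 66% or 44%. These SEs treat events as independent; clustering within couples would widen them.

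**4. Gain in precision from baseline adjustment.** The variance factor is 1 − ρ². For ρ = .1, .2, .3, .5 it is .99, .96, .91, .75. At 450 per group and an assumed standardized difference of .15, power rises from .614 to .618, .632, .655 and .738. The main benefit is therefore bias detection, not power.

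**5. Windows of numerator and denominator.** If conceptions are counted after RVN but years of marriage over the whole marriage, a man with 10 post-RVN years and 2, 5 or 10 pre-RVN years of marriage has his index multiplied by 10/12 = .83, 10/15 = .67 or 10/20 = .50.

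**The case against.** The strongest reply has five parts.

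- **The list is a minimum.** VI.D sets a lower limit on both the variables and the statistics, offers a fuller covariance analysis, and the data are kept. This stands: nothing is discarded, and a pre-RVN analysis is not excluded. A post-RVN definition of the primary variables is also legitimate. What the plan lacks is any stated use of the pre-RVN history.
- **Other safeguards exist.** V.D(2) compares medical records, including dependents' records, with questionnaire answers and seeks certificates for post-RVN offspring. XIII asks for the wife to be present and includes verification and bias-indicator questions. V.G and VI.H add regression on an exposure index. A reader might infer that a post-RVN excess could not be separated from over-reporting at all; these measures show that this goes too far. They do not supply a group-level baseline for miscarriages.
- **The control is not clean.** A reader might infer that a pre-RVN excess could arise only from reporting or selection. VIII.J says many of these men sprayed pesticides before Vietnam as well, VI.H expects domestic herbicide exposure, and chance remains. The pre-RVN ratio is evidence, not proof.
- **It can miss the bias.** Compensation and publicity, which VIII.D lists as motives, may inflate post-RVN reports selectively. A null pre-RVN ratio would then reassure falsely. Together with the low power shown above, this stands as a limit that must be stated.
- **Collection is inferred.** XIII does not mention pre-RVN pregnancies as such. The reading rests on an undated history that includes total conceptions, which is why the fix asks for timing to be recorded.

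A further tempting step is to argue from the TCDD half-life in IV.B(3) that most post-RVN years are nearly unexposed and should be split by time since RVN. The documents do not support it: the 12 to 50 days vary by species and come mostly from animals, no human half-life for TCDD is given, and IV.C hypothesises later release from fat.

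**Conclusion.** The concern holds as a weakness in the stated analysis that should be corrected. It is not a contradiction, and it does not invalidate the reproductive comparison. VI.D confines the primary reproductive variables to post-RVN questionnaire counts, adjusts only for years of marriage, and gives no role to a pre-RVN history that the interview should already yield. Exposed-only false reporting of a few per cent could by itself produce a noticeable relative risk, and for miscarriages the other safeguards are weakest.

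The gain from the change is real but moderate. It depends on over-reporting not being confined to post-RVN pregnancies and on enough couples having pregnancies before RVN. The conceptions per couple, miscarriage fraction, false positive rates and correlations are all assumptions; none is in the protocol.

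**What to change.** In VI.D, with a matching line in XIII:

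1. Record for each pregnancy whether it fell before or after the first RVN tour, with a stated rule for conceptions during a tour.
2. Compute the same variables for the pre-RVN period as for the post-RVN period, taking the counts and the years of marriage over the same window.
3. Use the pre-RVN values as covariates for the post-RVN variables.
4. Report the pre-RVN RANCH HAND/control ratio with its confidence interval beside each post-RVN ratio, as a negative control.
5. State its limits: it does not detect over-reporting confined to post-RVN pregnancies; some men had pesticide exposure before Vietnam; men without pre-RVN pregnancies contribute nothing to it; and its precision is modest, so an interval that includes 1 is not proof of unbiased reporting.

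No new provision is needed for certificates and records of post-RVN offspring, since V.D(2) largely covers it.

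The cost is one timing item per pregnancy in an interview already planned, plus analysis time. The timing item has to be in the questionnaire before interviewing starts, which the contact schedule in the Appendix puts at January 1980.

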Loss of participants over time adversely affects any epidemiologic study in two ways. As the sizes of the study groups decrease, statistical power also declines, and bias is injected into the study if losses are not randomly distributed in the study populations. It is reasonable to assume that in this study, losses will be non-random with greater non-compliance among individuals who perceive their health as "well," since there is less incentive for this group to continue participation. As shown in Figure 3, such a differential pattern of loss will alter the population and skew the frequency distribution curve.

Most previous epidemiologic studies have approached the problem of declining statistical power by beginning the study with multiple controls per exposed subject, and passively allowing attrition to occur throughout the study period. However, this approach does not address the problem of bias. This study will take an active approach to both of these problems by using a replacement concept. As a control is lost to study, a replacement will be chosen from the original set of 10 matched controls. The replacement will be selected from the control set, and will have a perception of health similar to that of the lost control (Figure 4). The replacement strategy will maintain statistical power and the integrity of the matched design despite loss to study in the control group, and will correct anticipated bias while minimizing the number of required physical examinations.

[figure not shown]
At the initiation of the follow-up study, loss of an exposed member will not be cause to cease surveillance of his primary matched control. In the event of a control loss (for reasons other than death), another control from the set will be brought to study (Figure 5), the comprehensive questionnaire will be administered, and a baseline physical examination performed. Medical data

EFFECT OF NON-RANDOM LOSS TO STUDY IN THE CONTROL POPULATION

- IF CONTROL LOSSES ARE ILL, A SPURIOUS EFFECT IS ATTRIBUTED TO HERBICIDE EXPOSURE.
- IF CONTROL LOSSES ARE WELL, A TRUE/VALID HEALTH EFFECT IS DILUTED.

ANALYSIS OF THE REPLACEMENT STRATEGY

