Survival analysis without covariates. The first step in the statistical analysis of survival data is descriptive, i.e., the construction of summary measures which provide a basis for comparing different exposure groups without any allowance for the effects of possibly confounding variables (e.g., age) except perhaps for some limited stratification. Since one must expect many "losses to follow-up", only methods which take full cognizance of this complication will be considered. It should be pointed out that all the methods described below assume independence between censoring (e.g.,

loss to follow-up) and death or morbid event, although some techniques permit different patterns of censoring in different exposure groups.

The life table method can be adapted to obtain a step-function approximation to survival distributions in the presence of censoring (Chiang, 1968, Gross and Clark, 1975). However, the product-limit estimator of Kaplan and Meier (1958) may be preferred due to its intrinsic properties and its relationship to more refined methods.

The failure time distribution is the function $F^0(t)$ which provides the probability of death at or before time t in the study. The Kaplan-Meier estimator of $F^0(t)$ is $\hat{F}^0(t)$ where

$$\hat{F}^0(t) = 1 - \prod_{i \in D(t)} [1 - 1/R(T_i)]$$

In this equation, $D(t)$ is the "death set" at time t , i.e., the set of all indices i of individuals who were observed to fail before time t . $R(T_i)$ is the number of individuals who were at risk just before time T_i , the time of death (or morbid event) of the i^{th} study individual in $D(t)$. This product-limit estimator of Kaplan and Meier is maximum likelihood in the class of all possible failure time distribution functions.

Assuming that failure time distributions have been calculated for RANCH HAND individuals and controls, the next question concerns testing the null hypothesis of equality between the distributions. When only two such distributions are being compared, one may use the nonparametric procedures generalizing Wilcoxon's statistic proposed by E. Gehan (1965a, b) and discussed by N. Mantel (1967). When more than two such distributions are being compared, one may use the nonparametric procedure generalizing the Kruskal-Wallis statistic proposed by N. Breslow (1970).

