Loss to study in the RANCH HAND group poses a major problem to the validity of the inferences that can be made from any subsequent comparisons between or within groups. The avenues of loss will conceivably arise from individual apathy (volunteer bias), lack of appropriate financial reimbursement for loss of salary, the presence or absence of illness (perception of health), and the lack of a desire for "treatment". Losses of matched controls during the questionnaire and physical examination phases of the study, though predictably greater than in the exposed group may be managed by replacement from the predetermined set of controls. The estimated participation of individuals is shown in Section XII, Figure A-3. It is estimated that the overall response rate of the exposed group will be 65% in the initial questionnaire and 40% in the physical examination phase of the study. These high non-compliance estimates are expected to occur despite great efforts to keep the questionnaire at an acceptable length, and to coordinate questionnaire administration and physical examination with the subject's personal schedule. Losses to study in either the exposed or control groups will obviously lead to decrements in statistical power, while losses in the control group could cause severe bias in the analytic phases of the study. Such losses would skew the distribution of controls, (Figures 3 and 4) and thus alter the characteristics of the population available for study. If differential losses in the control group occur (i.e., "well" controls dropout more frequently than "ill" controls), a "true" herbicide effect would be diluted (Figure 10). Conversely, if "ill" controls are differentially lost, a spurious effect would be attributed to herbicide exposure. To a lesser extent, losses in the exposed group could create similar effects; however, loss to study in the RANCH HAND population should be much less of a problem than in controls, due to their vested interest.

RATIONALE OF REPLACEMENT

DILUTIONAL BIAS

CONDITIONAL PROBABILITIES:

L = LOSS

W = WELL

I = ILL

(2) Corrective Measures

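### The survival methods in VI.E assume loss is independent of illness, V.E(3) expects loss to depend on health, and control replacement only partly closes the gap, so morbidity comparisons can be biased in either direction

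*Protocol*

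**What the plan says.** Protocol VI.E opens by applying survival methods to morbidity as well as to mortality. Under survival analysis without covariates it expects many losses to follow-up and promises that "only methods which take full cognizance of this complication will be considered". It then states that "all the methods described below assume independence between censoring" and death or morbid event. The one relaxation is that "some techniques permit different patterns of censoring in different exposure groups".

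V.E(3) says of the same losses that "losses will be non-random with greater non-compliance among individuals who perceive their health as" well. The figure text there gives both directions for controls: "IF CONTROL LOSSES ARE WELL, A TRUE/VALID HEALTH EFFECT IS DILUTED" and "IF CONTROL LOSSES ARE ILL, A SPURIOUS EFFECT IS ATTRIBUTED TO HERBICIDE EXPOSURE". VIII.G adds that "loss to study in the RANCH HAND population should be much less of a problem than in controls", although exposed losses could act similarly to a lesser extent.

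The countermeasure is in V.E(3), VI.I and VIII.G. A lost control is replaced by a man who "will have a perception of health similar to that of the lost control". Replacements are flagged. VI.I puts the analysis of intact pairs first and the analysis of all pairs second. VIII.G notes that the exposed group cannot be enlarged, so exposed losses are not replaced.

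**The concern.** The protocol predicts a loss mechanism and then relies, for time-to-event morbidity, on methods that it says exclude such a mechanism. Letting censoring differ by group does not resolve this, because loss must still be unrelated to the event within each group.

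If well men leave more often, those still under observation are increasingly the ones at higher risk, and one minus the Kaplan-Meier estimate becomes too high. If this happens unequally in the two groups, the Gehan and Breslow comparisons and the hazard models inherit the imbalance.

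Replacement acts on one group only. The intact-pair analysis and the all-pairs analysis can therefore err in opposite directions, and VI.E gives no means of telling which is nearer the truth. VI.E also leaves open how a replacement is counted. He enters late, and under V.E(3) his intervening years are reconstructed from questionnaire and interview.

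**Working it through.** The protocol gives no figure for this bias and no loss rates by health status, so both checks below are illustrations.

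**Inputs from the protocol.** Follow-up examinations are in years 3 and 5 (V.E(1)). Control loss per later examination is P2 = .25 (VI.I, Table 14). The printed C1 counts agree with that: 237/318 = .745 and 177/237 = .747 retained. Forty percent participation of 1200 men gives 480 (V.B, V.D(2)).

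**Assumptions not in the protocol.** 70% of men feel well and 30% feel ill. Event risk to year 3 is .03 (well) and .12 (ill), and from year 3 to year 5 it is .02 and .08. Control loss per examination is .30 well and .13 ill (range .28/.18 to .32/.08), which averages .7 × .30 + .3 × .13 = .249. RANCH HAND loss is 40% of that: .12 and .052. An event is seen only if the man attends. There is no true group effect.

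*True incidence.* Year 3: .7 × .03 + .3 × .12 = .0570. Year 5: (.679 × .02 + .264 × .08)/.943 = .0368. Cumulative: 1 − .9430 × .9632 = .0917.

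*Controls, losses treated as independent.* Year 3 attenders are .70 × .70 = .490 well and .30 × .87 = .261 ill. Risk = (.490 × .03 + .261 × .12)/.751 = .0613. Year 5 attenders are .490 × .97 × .70 = .3327 and .261 × .88 × .87 = .1998. Risk = (.3327 × .02 + .1998 × .08)/.5325 = .0425. Cumulative: 1 − .9387 × .9575 = .1012 (range .0972 to .1051).

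*Exposed, same method.* Year 3 risk is (.616 × .03 + .2844 × .12)/.9004 = .0584. Year 5 risk is .0387. Cumulative: .0948.

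*Ratios with no true effect.*
- Without replacement: .0948/.1012 = .94 (.91 to .96).
- Replacement restores the controls, exposed losses stand: .0948/.0917 = 1.03 (1.02 to 1.05).
- Equal loss by health in both groups: 1.00.

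*Scale.* The standard error of the group difference at 480 per group is √(2 × .0917 × .9083/480) = .0186. Without replacement the bias is (.1012 − .0948)/.0186 = .34 standard errors (range .20 to .48).

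**Second check, with a real effect.** VI.B(2) uses rates of .10 and .05, a relative risk of 2. For one examination interval, let lI and lW be the loss probabilities of men who did and did not fall ill in it. The observed risk is p(1 − lI)/[p(1 − lI) + (1 − p)(1 − lW)]. Control loss is held at .25 overall and lI is varied. For lI = .10, lW = (.25 − .05 × .10)/.95 = .258, and the control risk reads .045/(.045 + .705) = .060.

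| lI | No exposed loss | Exposed loss half | Exposed loss same | Controls restored, exposed half | Controls restored, exposed same |
|---|---|---|---|---|---|
| 0 | 1.50 | 1.70 | 1.97 | 2.27 | 2.62 |
| .10 | 1.67 | 1.80 | 1.98 | 2.16 | 2.38 |
| .25 | 2.00 | 2.00 | 2.00 | 2.00 | 2.00 |
| .40 | 2.50 | 2.30 | 2.02 | 1.84 | 1.62 |

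The direction depends on who is lost, on the relative loss in the two groups, and on whether replacement works.

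**The case against.** A reader might infer that VI.E is bound to overstate control incidence and dilute a true effect. The documents do not support that, for three reasons.

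- The protocol has a countermeasure aimed at this bias: health-matched replacement, flagged, with analyses run with and without it. VIII.D also promises models of anticipated biases before the final analysis of any phase.
- V.E(3) predicts health-dependent loss in the study populations generally. The exposed curve is overstated too, and equal loss rates leave the ratio almost unchanged.
- If replacement succeeds while exposed losses stand, the bias runs away from the null.

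Four further objections carry weight.

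- Feeling well is not the morbid event. Loss of well men biases a first-event curve only if they have a lower later hazard, or if attendance depends on illness since the previous contact.
- P2 covers all causes of non-compliance, including morbidity and mortality, so treating it as loss mainly of well men is an assumption.
- VI.E is permissive. Its hazard model takes time-varying covariates from an open list, so a health covariate would fit.
- Much questionnaire and examination morbidity is analysed under VI.D instead.

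These points limit the size and the direction. They leave the gap open: the intact-pair analysis gets no help from replacement, exposed losses cannot be replaced, perceived health is not among the covariates VI.E names, VIII.D names no method, and VI.E is silent on replacements in the risk sets. VI.I itself concedes that making replacements representative of non-compliant men will be difficult.

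**Conclusion.** The conflict between VI.E and V.E(3) is real, and the replacement scheme resolves it only in part. It matters for time-to-event morbidity, provided that lost men have a lower later hazard or that attendance depends on interval illness. It matters little for mortality, where vital status is traced whether or not a man participates.

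The illustrated bias is modest: a few percent on the ratio when there is no effect, and about a third of a standard error of the group difference without replacement. Those sizes rest on the assumed health split, event risks and loss rates, and on events being found only at attended examinations. The standard error ignores attrition below 480 per group, so the bias in standard-error units would be somewhat smaller than shown.

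The sign is not settled. The protocol's expectation of heavier control loss points to dilution in the intact-pair analysis, but the all-pairs analysis can err the other way.

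**What to change.** In VI.E, for morbid events:

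1. Weight each retained man, in both groups, by the inverse of his estimated probability of remaining. Estimate it from the Table 15 health and logistic factors and the compliance function D already planned in VI.I. Report the unweighted analysis alongside.
2. State how replacements enter the risk sets: from what date they count as at risk, and how their reconstructed years are used.
3. Limit the unqualified independence assumption to mortality.

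Do not stratify the group tests on perceived health at last contact. It is measured after exposure and may lie on the path from herbicide to disease. In the model above, suppose exposure did nothing except move men from 70/30 to 55/45 well/ill. True incidence would be .1129 against .0917, a ratio of 1.23, yet each stratum would show 1.0. Weighting does not condition the comparison on health in this way.

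The cost is wording and one weighted run on data already to be collected. The price is a slight loss of precision and reliance on the retention model, which corrects only for loss explained by the recorded factors.
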